### ANNEX 4: Classification of Treatment Outcomes (WHO, 2009)

Classification of treatment outcomes for plasmodium vivax malaria WHO

**Early Treatment Failure (ETF)**

- Danger signs or severe malaria on day 1, day 2 or day 3 in the presence of parasitemia;
- Parasitemia on day 2 higher than on day 0, irrespective of axillary temperature;
- Parasitemia on day 3 with axillary temperature  $\geq 37.5$  °C;
- Parasitemia on day 3  $\geq 25\%$  of count on day 0.

**Late Treatment Failure (LTF)*****Late Clinical Failure (LCF)***

- Danger signs or severe malaria in the presence of parasitemia on any day between day 4 and 42 in patients who did not previously meet any of the criteria of Early Treatment Failure;
- Presence of parasitemia on any day between 4 and day 42 with axillary temperature  $\geq 37.5$  °C (or history of fever) in patients who did not previously meet any of the criteria of Early Treatment Failure.

***Late Parasitological Failure (LPF)***

- Presence of parasitemia on any day between day 7 and day 42 and axillary temperature  $< 37.5$  °C in patients who did not previously meet any of the criteria of Early Treatment Failure or Late Clinical Failure.

**Adequate Clinical and Parasitological Response (ACPR)**

- Absence of parasitemia on day 42 irrespective of axillary temperature, in patients who did not previously meet any of the criteria of Early Treatment Failure, Late Clinical Failure, or Late Parasitological Failure.

Definition of Treatment Outcomes for *P. vivax* infections, WHO 2009

Treatment success:

the absence of parasitaemia on day 28/42, irrespective of axillary temperature, in patients who did not previously meet any of the criteria of treatment failure.

### Treatment Failure (TF)

Clinical deterioration due to *P. vivax* illness requiring hospitalization in the presence of parasitemia

Presence of parasitemia and axillary temperature  $\geq 37.5^{\circ}\text{C}$  on any day between day 3 and day 28/42

Presence of parasitemia on any day between day 7 and day 28/42, irrespective of clinical condition

## ANNEX 5: Drug Dosing and Regimens

All patients will be weighed to determine the accurate weight-based dose for all drugs.

- **Chloroquine:** Total of 25mg base per kg over 3 days (10 mg base/kg on Days 1 and 2, and 5 mg base/kg on Day 3). 500 mg tablets. We will use the syrup (10mg/ml) formulation for children < 4 years of age, if available.

Weight (kg)	Age	Day 1	Day 2	Day 3
5–6	<4 mo	¼ tablet (5 ml syrup)	⅛ tablet (5 ml syrup)	⅛ tablet (2.5 ml syrup)
7–10	4–11 mo	¼ tablet (7.5 ml syrup)	¼ tablet (7.5 ml syrup)	¼ tablet (5 ml syrup)
11–14	1–2 yrs	½ tablet (12.5 ml syrup)	½ tablet (12.5 ml syrup)	¼ tablet (7.5 ml syrup)
15–18	3–4 yrs	½ tablet (15 ml syrup)	½ tablet (15 ml syrup)	½ tablet (15 ml syrup)
19–24	5–7 yrs	¾ tablet (20 ml syrup)	¾ tablet (20 ml syrup)	½ tablet (15 ml syrup)
25–35	8–10 yrs	1¼ tablet	1¼ tablet	½ tablet
36–50	11–13 yrs	1½ tablet	1½ tablet	1 tablet
> 50	14+ yrs	2 tablet	2 tablet	1 tablet

--	--	--	--	--

**Primaquine:** 7.5 mg base tablet. Medication given as 0.25mg/kg daily for 14 days in people with normal G6PD levels. In people with G6PD deficiency, 0.75 mg/kg (45 mg) once a week for 8 weeks.

Body Weight (kg)	Single dose of primaquine (mg base)
5 to 10	Weight-based using extemporaneous preparation as outlined by Sanofi
10 to < 25	3.75
25 to <50	7.5
50 to 100	15

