## **Treatment**

### **Antimalarial Treatment**

*P. vivax* patients will receive CQ+PQ. The correct drug doses will be determined by the dosing chart (Annex III). All drugs administered in the facility will be under supervision by the staff. Patients will be observed for 60 minutes after treatment for adverse reactions or vomiting. Those patients vomiting their medication within the first 30 minutes will receive a repeat full dose, while those vomiting from 30-60 minutes will receive half dose. Patients who vomit twice will be referred to higher level of care for management with parenteral artesunate therapy and withdrawn from the study. This is standard practice for anti-malarial treatment. All study drugs will be obtained from WHO Ethiopia office through Ethiopian Pharmaceutical Supply Agency.

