### Body Weight

Body weight will be recorded on day 0 to the nearest kilogram on a scale or on a hanging scale for young children. The scales will be properly calibrated. Patients should not wear excessive clothing while being weighed as this can overestimate their true weight. All young children should only wear undergarments while being weighed. The screening weight will be used to satisfy the inclusion or exclusion criteria for weight and nutrition status as well as to calculate the dose (number of tablets) to be administered. The reliability of the scales will be verified before the study begins and checked at regular intervals.

The circumference of the left mid-upper arm will be measured, at the mid-point between the elbow and the shoulder and will be recorded to the nearest 0.2 cm. Oedema will be assessed by thumb pressure for 3 seconds on the dorsal surface of both feet.

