#### **Day 2:**

---

- Clinical assessment — referral in case of severe malaria/danger signs
- Measurement of axillary temperature
- Blood sampling for blood smears and filter paper
- Treatment, third dose or alternative treatment in case of early treatment failure

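### Annex 5's chloroquine chart gives three equal doses at 15-18 kg, and in the 7-10 kg tablet column, where its own 10/10/5 mg base/kg rule halves the third

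*Combined protocol and SAP*

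**What the plan says.** Annex 5 gives the chloroquine rule as "Total of 25mg base per kg over 3 days (10 mg base/kg on Days 1 and 2, and 5 mg base/kg on Day 3", followed by the products: "500 mg tablets. We will use the syrup (10mg/ml) formulation for children < 4 years of age, if available". Neither strength is marked as base or salt, whereas the primaquine tablet in the same annex is marked as base.

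The chart below the rule lists tablets, and syrup for the lighter bands, by weight. At 15-18 kg the cell "½ tablet (15 ml syrup") appears on all three days. At 7-10 kg the tablet entry is ¼ on all three days, while the paired syrup falls from 7.5 ml on Days 1 and 2 to 5 ml on Day 3 ("¼ tablet (5 ml syrup")).

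The chart is what staff dose from. The Antimalarial Treatment section says "The correct drug doses will be determined by the dosing chart (Annex III"), and the Body Weight section uses screening weight "to calculate the dose (number of tablets) to be administered". The only dosing chart shown is in Annex 5, so the pointer to Annex III is a clerical slip.

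The chart's Day 3 is the dose that Annex 8 schedules on study Day 2: "Treatment, third dose or alternative treatment in case of early treatment failure".

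**The concern.** The rule and the chart sit in the same annex and disagree. The rule makes the third dose half of the first. In two places the chart makes it equal to the first, and that ratio does not depend on the tablet or syrup strength. Since the chart decides what is given, children in those bands would not receive the stated regimen.

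Both formulations can matter at 15-18 kg: the chart's age for that row is 3-4 years, and syrup is meant for children under 4 where it can be had. The 7-10 kg tablet column (chart age 4-11 months) matters only when syrup is not available.

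What is at stake is whether the dose under test is the one the protocol describes. An efficacy estimate from directly observed treatment should rest on a dose in mg base/kg that a reader can confirm from the text.

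**Working it through.** **Inputs from Annex 5:** rule 10/10/5 mg base/kg; syrup 10 mg/ml; the tablet fractions and syrup volumes by weight band.

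**Assumptions, not in the documents:** the 10 mg/ml is base; a tablet holds 300 mg base. The 15-18 kg row supports the second if the first holds: 15 ml × 10 = 150 mg is paired with ½ tablet, so 150 / 0.5 = 300 mg.

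**Formula:** mg/kg = amount in mg / weight, taken at the top and bottom of each band.

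**The rule itself:** 10 + 10 + 5 = 25 mg/kg, third-to-first ratio 5/10 = 0.5. This is consistent.

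**15-18 kg as printed** (150 mg each day, by syrup or by tablet at 300 mg base):
- Each day: 150/18 = 8.3 to 150/15 = 10.0 mg/kg.
- Third dose against 5: 8.33/5 = 1.67 to 10/5 = 2.00, so 67-100% over.
- Total: 450/18 = 25.0 to 450/15 = 30.0 mg/kg, so 0-20% over.
- Third-to-first ratio: 1.0 against 0.5.

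A fixed volume over this band must vary by a factor of 18/15 = 1.2, so a 20% spread is unavoidable. An excess of 67-100% is well outside it.

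**7-10 kg tablets as printed** (¼ tablet = 75 mg each day at 300 mg base):
- Each day: 75/10 = 7.5 to 75/7 = 10.7 mg/kg.
- Third dose against 5: 7.5/5 = 1.50 to 10.71/5 = 2.14, so 50-114% over.
- Total: 225/10 = 22.5 to 225/7 = 32.1 mg/kg.

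**Does rounding force the equal doses?**

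Syrup volumes in the chart move in 2.5 ml steps, and in every other row with syrup the volume falls on Day 3. Two alternatives on those steps at 15-18 kg:

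| Syrup (ml) | Days 1 and 2 (mg/kg) | Day 3 (mg/kg) | Total (mg/kg) |
|---|---|---|---|
| 15/15/15 (printed) | 8.3-10.0 | 8.3-10.0 | 25.0-30.0 |
| 17.5/17.5/10 | 175/18 = 9.7 to 175/15 = 11.7 | 100/18 = 5.6 to 100/15 = 6.7 | 450 mg: 25.0-30.0 |
| 17.5/17.5/7.5 | 9.7-11.7 | 75/18 = 4.2 to 75/15 = 5.0 | 425/18 = 23.6 to 425/15 = 28.3 |

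So the syrup entry is not forced.

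Tablets at 15-18 kg (300 mg base) do face a trade-off. ½/½/¼ restores the split but totals 375/18 = 20.8 to 375/15 = 25.0. ¾/¾/¼ totals 525/18 = 29.2 to 525/15 = 35.0, with Days 1 and 2 at 225/18 = 12.5 to 225/15 = 15.0. At 7-10 kg, ¼/¼/⅛ (eighths appear in the 5-6 kg row) would give 37.5/10 = 3.8 to 37.5/7 = 5.4 on Day 3, but a total of only 187.5/10 = 18.8 to 187.5/7 = 26.8.

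**25-35 kg tablets** (1¼/1¼/½ at 300 mg base): Days 1 and 2 375/35 = 10.7 to 375/25 = 15.0; Day 3 150/35 = 4.3 to 150/25 = 6.0; total 900/35 = 25.7 to 900/25 = 36.0. Here the third dose is close to the rule, but the total runs high.

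**Why the label matters:** if 500 mg were read as base, ½ tablet three times is 750 mg, and 15-18 kg would total 750/18 = 41.7 to 750/15 = 50.0 mg/kg.

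**The case against.** The best defence is that the printed 15-18 kg row reaches the course total (25.0-30.0 mg/kg) with no day above 10 mg/kg, and that equal tablet doses are a sensible compromise when the alternatives fall short or overshoot. For the tablet entries this stands: they may be deliberate. But the annex states no rounding rule or exception, so staff cannot tell a compromise from an error. For syrup it does not stand, because finer steps were available and are used elsewhere in the chart.

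Three stronger readings are tempting, and the documents do not support them.

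- **That tablet and syrup strengths are mutually inconsistent.** Dividing syrup mg by tablet fraction gives values from 200 to 400 mg per tablet. But each amount is rounded separately. At 11-14 kg the first-dose target is 110-140 mg: "½ tablet (12.5 ml syrup") pairs 150 mg (at 300 mg per tablet) with 125 mg of syrup, and each is a reasonable rounding. The spread is mostly that, and it does not show that different products are meant.
- **That tablets could hold 200 mg and underdose.** The 15-18 kg pairing itself gives 300 mg. At 200 mg, the 36-50 kg row would give only 300/50 = 6.0 to 300/36 = 8.3 mg/kg on Days 1 and 2 against 10, so the chart does not fit that strength.
- **That the chart cannot be matched to any product.** Reading the syrup as base and the tablet as about 300 mg base makes most rows roughly right. The missing label calls for clarification and does not make the chart unusable.

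**Conclusion.** The chart departs from its own rule in the 15-18 kg row and the 7-10 kg tablet column. The equality of the three doses holds at any strength. The sizes rest on assumptions: 67-100% over at the third dose for 15-18 kg if 10 mg/ml is base, and 50-114% over for 7-10 kg tablets at 300 mg base. An extraction fault is unlikely at 15-18 kg, where the same pair of values appears three times.

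The 25-35 kg row deserves a check for its total (25.7-36.0 mg/kg at 300 mg base), but it is not the largest departure on the third dose.

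A reader might infer a toxicity risk or a bias in the failure proportion. Neither follows. At 15-18 kg no single dose exceeds the 10 mg/kg that the rule allows on Days 1 and 2, and the total is at most 20% over. The documents give no weight distribution, so the number of children affected is unknown. The sample size is unaffected. This is an error in the operative dosing table that should be fixed and is cheap to fix.

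**What to change.** - Correct the 15-18 kg syrup volumes to follow 10/10/5, for example 17.5/17.5/10 ml (keeps the 25.0-30.0 total) or 17.5/17.5/7.5 ml (third dose at or below 5, total 23.6-28.3). Lowering Day 3 alone to 7.5 ml would cut the total to 375/18 = 20.8 to 375/15 = 25.0, so Days 1 and 2 should move with it.
- Recheck the equal-day tablet entries (7-10 and 15-18 kg) and the 25-35 kg row against 10/10/5. Either correct each one or state in the annex that it is a rounding exception.
- Give the tablet and syrup strengths in mg base.
- Point the Antimalarial Treatment section to Annex 5.

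The cost is one table revision, two labels and a cross-reference, with final doses confirmed by the sponsor's clinicians. Visits, sample size and analysis do not change.

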### Study Design

This Therapeutic Efficacy study is a prospective evaluation of clinical and parasitological responses to directly observed treatment for uncomplicated vivax malaria (51,52). People with uncomplicated plasmodium vivax malaria who meet the study inclusion criteria will be enrolled and treated on site with Chloroquine plus Primaquine for *p.vivax* infection and monitored up to 42 days.

The follow-up will consist of a fixed schedule of check-up visits and corresponding clinical and laboratory examinations. On the basis of the results of these assessments, the patients will be classified as having therapeutic failure (early or late) or an adequate response.

The proportion of patients experiencing therapeutic failure during the follow-up period will be used to estimate the efficacy of the study drugs. Molecular analyses will be used to distinguish between a true recrudescence due to treatment failure and episodes of reinfection as well as determine polymorphisms of known resistance markers. In addition, drug level testing may be conducted depending on the availability of resources. .

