#### **Patient Discontinuation or Protocol Violation**

Patients meeting any of the following criteria will be withdrawn:

- Withdrawal of consent
- Failure to complete the treatment
  - Vomiting both initial and replacement doses at any single time in the treatment (i.e. If the patient vomits both attempts to administer the morning dose that would

- require withdrawal; however, vomiting the initial morning dose but not the morning replacement dose would not require withdrawal), persistent vomiting
- Severe side-effects necessitating hospitalization
  - Progression to severe malaria
  - Failure to attend the scheduled visit during the first 3 days
  - Enrolment violation
    - Severe malaria on day 0
    - Erroneous inclusion of a patient outside of the inclusion/exclusion criteria
  - Voluntary protocol violation: Antimalarial (or antibiotics with antimalarial activity) treatment administered by a third party or self-medication with antimalarial (or antibiotics with antimalarial activity) assessed by asking participants or their caretaker at follow-up visits (Annex VI)
  - Involuntary protocol violation
    - Occurrence during the follow-up of concomitant disease that would interfere with a clear classification of the treatment outcome
    - Detection of a mono-infection with another malaria species during follow-up
    - Misclassification of a patient due to a laboratory error (parasitemia) leading to the administration of the rescue treatment

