5. After assignment, on day 0, each patient will receive the dose of treatment medication under direct observation and will be monitored for vomiting. Each patient will return on days 1 and 2 for subsequent doses. Clinical reassessments will be made on days 1- 3, 7, 14, 21, 28, 35, and 42 (see Annex VI). Participants will be given 100 Ethiopian Birr for each visit to cover their travel expenses (this is a compensation for a round-trip transportation to the clinic). Patients will be advised to return on *any* day during the follow-up period if symptoms return and not to wait for scheduled visit days. Patients who do not present to the facility for follow-up visits will be followed at home. This is standard for *in vivo* studies based on the WHO protocol, but is not the standard for routine care. Typically, for patients not enrolled in a study, the parent would be given all the doses of the medicine to administer at home, and no follow-up would be scheduled. The parent would be told to return if they did not improve.
6. Blood films (thick and thin) for parasite count and dried blood spot will be obtained and examined as described above. All samples will have the study ID number and date of collection, but no other personal identifiers. The logbook that links the study ID number to the patient will be kept at the study site locked in a cabinet when not in use during the study enrollment period. After the completion of the study, this logbook will be stored at EPHI.
7. If patients do not appear for scheduled follow-up, the study team will attempt to reach them at home. After day 3, patients who fail to return on their scheduled day but return one day early or one day late may still be included in the analysis.
8. A case report form will be used to record the general information and clinical observations on each patient enrolled into the study. The appointment schedule will be clearly explained, and a follow-up card with a personal identification number will be provided. The study schedule (Annex VI) and follow-up schedule is summarized in (Annex VII).

**Storage of specimens:** Specimens obtained in this study will be saved for the duration of specified testing. Specimens will not be tested for HIV.

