## ANNEX 9: Schedule of Follow-Up Activities

	day 0	day 1	day 2	day 3	day 7	day 14	day 21	day 28	day 35	day 42	any other day
PROCEDURES											
Clinical assessment	X	X	X	X	X	X	X	X	X	X	X
Temperature	X	X	X	X	X	X	X	X	X	X	X
Blood slide for parasites count	X	X	X	X	X	X	X	X	X	X	X
Hemoglobin	X					X		X		X	X
Filter paper	X			X	X	(X)	(X)	(X)	(X)	(X)	X
Drug adverse event monitoring	X	X	X	X	X	X	X	X	X	X	X
TREATMENT											
Drug to be given	X	X	X								(X)
Rescue treatment		(X)	(X)	(X)	(X)	(X)	(X)	(X)	(X)	(X)	(X)

NOTES: Parentheses denote conditional or optional activities. Rescue treatment could be given on any day, provided that the patient meets the criteria for treatment failure. Extra days are any days other than regularly scheduled follow-up days when the patient returns to the facility because of recurrence of symptoms.

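### Primaquine is prescribed for 14 days or 8 weeks by G6PD status, but study drug is scheduled only on days 0 to 2, completion of primaquine is undefined, and no legible text obtains G6PD status

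*Combined protocol and SAP*

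**What the plan says.** Annex 5 gives two primaquine regimens. The first is "Medication given as 0.25mg/kg daily for 14 days in people with normal G6PD levels". The second, for G6PD deficiency, is 0.75 mg/kg once weekly for 8 weeks.

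The dosing schedule is shorter. After the day 0 dose, Enrollment and Follow-up (item 5) says: "Each patient will return on days 1 and 2 for subsequent doses". Annex 8 ends dosing on day 2 with "Treatment, third dose or alternative treatment in case of early treatment failure", and its entry for days 3 to 42 lists no study dose. In Annex 9 the row "Drug to be given" is marked on days 0, 1 and 2. Its only other mark is a conditional one under unscheduled days, which the note explains: "Extra days are any days other than regularly scheduled follow-up days when the patient returns to the facility because of recurrence of symptoms".

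Study Design calls the trial a "prospective evaluation of clinical and parasitological responses to directly observed treatment for uncomplicated vivax malaria" and places treatment on site.

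Among the withdrawal criteria is "Failure to complete the treatment". The items beneath it concern vomiting. The Statistical Analysis section uses Kaplan-Meier and per-protocol analyses for the primary outcomes and treats withdrawals as censored in the former. It does not define the per-protocol set.

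**The concern.** The two parts of the plan do not agree on how a study drug is given. The day 0 to 2 schedule fits the three-day chloroquine course, and nothing legible extends it to primaquine. Yet Study Design, Study Population and Dependent Variables make the combination the treatment under evaluation, and the Background credits it with preventing relapse. Annex 4 counts parasitaemia from day 7 to day 42 as failure. Without a record of which primaquine doses were taken, a recurrence cannot be read against the treatment received.

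There are two further consequences. First, a patient who stops primaquine on day 5 may be withdrawn by one member of staff and kept by another, because the completion criterion does not mention primaquine. That choice carries into both primary analyses. Second, each regimen is conditional on G6PD status, so staff without that status cannot assign either one as written.

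**Working it through.** The plan states no dose count to reproduce, and the sample size plays no part here. The check sets the regimens against the calendar.

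**Inputs**
- Regimens (Annex 5): 14 daily doses of 0.25 mg/kg, or 8 weekly doses of 0.75 mg/kg.
- Drug days (Enrollment and Follow-up, Annexes 8 and 9): 0, 1, 2.
- Visit days (same sources): 0, 1, 2, 3, 7, 14, 21, 28, 35, 42.
- Start of primaquine: not stated; day 0 is assumed.

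**Daily regimen, days 0 to 13**
- On drug days: 0, 1, 2, so 3 of 14. Not scheduled: 14 − 3 = 11, and 11/14 = 79%.
- On any visit day: 0, 1, 2, 3, 7, so 5 of 14.
- On days with no visit: days 4 to 6 (3 doses) and 8 to 13 (6 doses), so 9 of 14, or 64%.
- Dose covered by the schedule: 3 × 0.25 = 0.75 mg/kg of 14 × 0.25 = 3.5 mg/kg, or 21%.

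**Weekly regimen, days 0, 7, ..., 49**
- On drug days: day 0 only, so 1 of 8.
- On visit days: 0, 7, 14, 21, 28, 35, 42, so 7 of 8.
- The eighth dose is on 7 × 7 = day 49, seven days after follow-up ends.

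**Sensitivity to the start day.** If the daily course starts on day 2 (days 2 to 15), 1 of 14 doses is on a drug day and 4 of 14 (days 2, 3, 7, 14) are on visit days. A later start leaves fewer doses covered.

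**Completion.** The withdrawal list specifies vomiting of initial and replacement doses, and separately missed visits in the first three days. Neither says whether a primaquine dose missed after day 2 makes treatment incomplete.

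**G6PD.** The term appears only in Annex 5. It is absent from the eligibility criteria, laboratory examination, blood sampling, enrolment steps, screening form and both schedules. The enrolment steps assign the filter paper to molecular testing and drug levels, without naming G6PD.

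**The case against.** The best reply is that primaquine after day 2 is simply meant to be taken at home. The Antimalarial Treatment section supervises only doses given in the facility, which leaves room for that. But no legible text tells anyone to dispense or record home doses, Study Design describes observed treatment, and Enrollment and Follow-up presents home dosing as what happens to patients outside the study. On this reading the defect is an unwritten instruction and a missing dose record, which still needs repair.

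A second reply is that completion means the day 0 to 2 doses, since the first three days have their own attendance rule. That is plausible, but the plan does not say so.

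A third is that molecular analysis and drug levels would help to interpret a recurrence. They help in part. However, "drug level testing may be conducted depending on the availability of resources", and neither shows which doses were taken.

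Some stronger readings are not supported:
- A reader might infer that 11 of 14 doses will go ungiven or unrecorded. Rows 1, 2 and 6 of the follow-up form are illegible, the enrolment form has an item for the tablet count, and consent pages are not available. The supported statement is that no legible text schedules or records those doses.
- A reader might infer that incomplete primaquine would use up the 15-patient allowance for attrition. The documents give no rate of missed doses, and Kaplan-Meier keeps a withdrawn patient until censoring.
- A reader might infer that a G6PD test must be added. An existing source of status, or a rule for unknown status, would also close the gap.

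**Conclusion.** The point holds. As written, the schedule covers 3 of 14 daily primaquine doses or 1 of 8 weekly doses, given a day 0 start. Nine of the 14 daily doses fall on days without a visit, and the last weekly dose falls outside follow-up. Completion of primaquine is undefined, and G6PD status has no legible source. This should be settled before enrolment, because dose assignment, dose records and the handling of patients in both primary analyses depend on it.

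Two limits apply. That withdrawn patients leave the per-protocol set is the ordinary reading, not something the plan states. And a reader might infer that the cure rate is biased in a known direction, but the documents do not allow its size or direction to be worked out. The effect would be smaller if the Classification of Treatment Outcomes section governs, since it names only chloroquine for *P. vivax*. The point takes no position on which primaquine regimen is right.

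**What to change.** 1. **Schedule and record the doses.** Add every primaquine dose to Enrollment and Follow-up item 5 and to Annexes 8 and 9. For the daily regimen, observe the doses on days 0 to 3 and 7, have the other nine taken at home, and log them on the case report form: days 4 to 6 at the day 7 visit, and days 8 to 13 at the day 14 visit. For the weekly regimen, say how the day 49 dose is handled. Limit the direct-observation claim in Study Design to observed doses. Amend the contrast with home dosing in item 5, and exempt study chloroquine and primaquine from the Annex 7 list of drugs not to be used.
2. **Define completion.** In Patient Discontinuation or Protocol Violation, state an explicit primaquine rule, and apply it to both primary analyses in Statistical Analysis.
3. **Settle G6PD.** State the existing source of G6PD status, or give one primaquine rule for unknown status, with follow-up for haemolysis at the haemoglobin visits already planned (days 0, 14, 28 and 42). Removing only the weekly option would not be enough, because the daily course is itself limited to normal G6PD.

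The cost is text changes, a small amount of record-keeping, and disclosure in the report that up to nine doses per patient were unobserved. No visits are added. A new G6PD test would be an extra procedure, for which the documents give no cost; this fix does not require it.

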### **Study Variables**

#### **Independent Variables**

- Age, Sex, Weight, Axillary temperature, leukocyte count, asexual and/ or sexual parasites count, Hemoglobin count

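### The Annex 5 primaquine chart runs from 40% below to 50% above the stated 0.25 mg/kg daily, and 11 of the 14 daily doses appear in no schedule

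*Combined protocol and SAP*

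**What the plan says.** Annex 5 (Drug Dosing and Regimens) promises an accurate dose by weight for every drug. For primaquine it gives a 7.5 mg base tablet and "Medication given as 0.25mg/kg daily for 14 days in people with normal G6PD levels". Patients with G6PD deficiency have a separate weekly course: "In people with G6PD deficiency, 0.75 mg/kg (45 mg) once a week for 8 weeks".

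One chart follows, headed "Single dose of primaquine (mg base". It gives an individually prepared dose at 5 to 10 kg, 3.75 mg at 10 to under 25 kg, 7.5 mg at 25 to under 50 kg, and 15 mg at 50 to 100 kg.

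The Antimalarial Treatment section makes the chart the operative instruction: "The correct drug doses will be determined by the dosing chart (Annex III". The dosing charts are in fact in Annex 5.

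On timing, Enrollment and Follow-up says: "Each patient will return on days 1 and 2 for subsequent doses". Annex 8 ends study treatment with a third dose on day 2. Annex 9 marks study drug on days 0, 1 and 2, leaves days 3 to 42 blank, and has a conditional entry under any other day. Study Design describes a "prospective evaluation of clinical and parasitological responses to directly observed treatment for uncomplicated vivax malaria".

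**The concern.** The stated regimen and the chart that staff will follow disagree within one annex, and the schedules stop long before a 14-day course ends.

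The Dependent Variables section names the efficacy of chloroquine plus primaquine. If the chart prescribes a clearly different dose at some weights, the result will be reported for a regimen that those patients were not prescribed. The protocol's own Statement of the Problem names optimal dosage and duration as the open question.

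The missing days also bear on the analysis. Failure to complete treatment is a ground for withdrawal, and the Statistical Analysis section relies partly on a per-protocol analysis. With days 3 to 13 in no schedule, the plan does not show how completion of primaquine would be judged.

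**Working it through.** **Inputs.** The target dose, tablet strength and chart rows are from Annex 5. Weights are whole kilograms: "Body weight will be recorded on day 0 to the nearest kilogram". Dosing days are from Enrollment and Follow-up, Annex 8 and Annex 9.

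**Is the chart a daily amount?** At 60 kg, 0.25 × 60 = 15 mg, which is the chart's entry. The weekly dose at 60 kg would be 0.75 × 60 = 45 mg, which appears nowhere in the chart. So the daily reading fits, although the column heading does not say so.

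**Plan's own figure.** 0.25 mg/kg × 14 days = 3.5 mg/kg in total. The chart reproduces 0.25 mg/kg at 3.75/0.25 = 15 kg, 7.5/0.25 = 30 kg and 15/0.25 = 60 kg, and at no other whole-kilogram weight in the fixed-dose rows.

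**Departure** = (chart dose / weight) / 0.25 − 1:

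| Row | Dose | Lower end | Upper end |
|---|---|---|---|
| 10 to under 25 kg | 3.75 mg | 10 kg: 0.375 (+50%); 11 kg: 0.341 (+36%) | 24 kg: 0.156 (−37.5%) |
| 25 to under 50 kg | 7.5 mg | 25 kg: 0.300 (+20%) | 49 kg: 0.153 (−39%) |
| 50 to 100 kg | 15 mg | 50 kg: 0.300 (+20%) | 100 kg: 0.150 (−40%) |

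If 10 kg goes to the weight-based row, the largest excess is +36%, at 11 kg. The 14-day total runs from 14 × 0.150 = 2.10 to 14 × 0.375 = 5.25 mg/kg, against 3.5.

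**More than 20% low** means below 0.20 mg/kg, so weight above dose/0.20: 18.75, 37.5 and 75 kg. In whole kilograms that is 19-24 kg (0.197 to 0.156), 38-49 kg (0.197 to 0.153) and 76-100 kg (0.197 to 0.150).

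**Steps between rows.** From 24 to 25 kg: 0.300/0.15625 = 1.92-fold. From 49 to 50 kg: 0.300/0.15306 = 1.96-fold.

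**Would a 15 mg maximum explain it?** A maximum bites only where 0.25 × weight exceeds 15 mg, that is above 60 kg. At 38-49 kg the target is 9.5 to 12.25 mg; at 19-24 kg it is 4.75 to 6.0 mg. Neither reaches 15 mg.

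**Would tablet rounding explain it?** The chart already uses half tablets, in steps of 3.75 mg. The midpoint of 7.5 and 11.25 is 9.375 mg (37.5 kg), and that of 11.25 and 15 is 13.125 mg (52.5 kg). The nearest half-tablet dose at 38-52 kg is therefore 11.25 mg, giving 11.25/38 = 0.296 to 11.25/52 = 0.216 mg/kg. The midpoint of 3.75 and 7.5 is 5.625 mg (22.5 kg), so 3.75 mg is the nearest dose up to 22 kg.

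**Schedule.** A 14-day course starting on day 0 covers days 0-13. Three days are planned, so 14 − 3 = 11 are not. The note to Annex 9 limits extra days to returns for recurrent symptoms, so the conditional entry does not supply the course.

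**The case against.** Banded dosing with a 7.5 mg tablet always departs from an exact mg/kg figure, and a flat 15 mg at the top may be intended. Part of this stands: the shortfall above 60 kg may be deliberate, and at 19-22 kg the 3.75 mg dose is the nearest half-tablet amount. It does not cover 38-49 kg, where one and a half of the stated tablets comes closer.

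The schedule gap can also be read as an omission. Annex 5 states 14 days outright, and Antimalarial Treatment promises supervision only of drugs given in the facility, which leaves room for doses elsewhere. That is fair. A reader might infer that patients receive only three primaquine doses, or a single-dose course; the stated 14 days contradicts both. Nor do the documents say that the remaining doses are taken at home, or how many are observed.

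The Classification of Treatment Outcomes section names chloroquine alone for *P. vivax*, so primaquine dose might seem secondary. But that text also covers *P. falciparum* and other drugs and appears carried over, while Dependent Variables names the combination.

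Finally, prescribed mg/kg can be worked out later, since weight is among the recorded variables ("Age, Sex, Weight, Axillary temperature, leukocyte count"). That describes the shortfall but does not restore the dose.

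**Conclusion.** The point holds and should be fixed before first dosing. Read as a daily amount, the chart runs from 40% below to 50% above the stated dose (+36% at most if 10 kg is weight-based), with 21% to 39% shortfalls at 19-24 kg and 38-49 kg that a maximum dose cannot explain. Eleven of 14 daily doses are unplanned. The divisions are certain. The daily reading of the chart is an inference, and the count of 11 assumes a day 0 start.

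Two larger claims are tempting and unsupported. One is that a particular share of patients would be underdosed: the documents give no weight distribution, and any percentage would follow from the weights assumed. The other is that the day-42 failure rate would be shifted by a known amount: the documents give no dose-response.

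**What to change.** Before first dosing:

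1. Head the column as the daily dose for 14 days, place 10 kg in one row only, and correct the Annex III reference in Antimalarial Treatment.
2. Keep 7.5 mg for 25-37 kg (0.300 to 7.5/37 = 0.203 mg/kg), add 11.25 mg (one and a half tablets) for 38-52 kg (0.296 to 0.216), and give 15 mg from 53 kg (15/53 = 0.283). State whether 15 mg is the maximum; if not, heavier patients need further rows. Below 25 kg, extend the weight-based preparation already used at 5-10 kg if it can be supplied. Otherwise keep the tablet row and state the residual departure: 0.341 at 11 kg to 0.156 at 24 kg. Moving 23-24 kg up to 7.5 mg would only exchange the shortfall for an excess of 30% and 25%.
3. Show primaquine on days 0-13 in Enrollment and Follow-up and in Annexes 8 and 9, and state which doses are observed and which are taken at home. If the existing visits on days 0, 1, 2, 3 and 7 are used for observation, 14 − 5 = 9 are unobserved, and the directly observed description in Study Design should say so.
4. Report prescribed primaquine mg/kg beside treatment failures, and describe the tested regimen by the dose actually prescribed.

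**Cost.** An amendment to one annex, one cross-reference and the drug schedule, with clinical agreement on the rows and the maximum. Patients of 50-52 kg move down from 0.288-0.300 to 0.216-0.225 mg/kg. No visits are added if 9 doses are accepted as unobserved. Observing all 14 at the clinic would add 9 contacts: 9 × 100 = 900 Birr per patient in travel payments, or 900 × 88 = 79,200 Birr for the planned 88 patients.
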